1. SUMMARY OF THE STUDY

Background. Laparoscopic cholecystectomy is one of the most commonly performed surgical procedures worldwide. One of its most serious complications is injury to the main bile duct, with an incidence of less than 1%. There are different surgical strategies that attempt to reduce this complication, with indocyanine green fluorescence cholangiography being one of the most recent to appear. This technique is becoming a great tool during laparoscopic cholecystectomy. Despite the boom in the procedure, there is currently a wide disparity in the protocols for administration of indocyanine green during the procedure.

Objectives. The main objective of the study is to analyse whether there are differences between different types of doses and administration intervals of indocyanine green to obtain quality fluorescein cholangiography during laparoscopic cholecystectomy. In addition, factors influencing the results of the technique will be sought.

Material and Methods. Open multicentre randomised clinical trial with 4 intervention groups (two doses and two administration times). The expected duration of the study will be 12 months. The main variables to be studied will be the degree of identification critical anatomical structures during laparoscopic cholecystectomy. Patients will be analysed per protocol, without intermediate analyses.

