20.12. Report to researchers

The sponsor will submit safety information that could impact the safety of the patients enrolled in the trial to the investigators as early as possible. In addition, the investigator will be informed throughout the study of any safety issues, including protocol modifications due to safety concerns.

21. Statistics

For the calculation of the sample size we estimated an average annual number of laparoscopic cholecystectomies of 300 cases. Assuming a minimum recruitment rate of 50% in the study, a duration of 12 months and possible losses of patients, we estimate a sample size of 200 patients.

Since the main objective is to analyse whether there are differences between the doses and administration times of the 4 treatment groups in which categorical variables will be measured, the effect of the chosen sample size ($n=200$) on the statistical contrasts in this type of variables is $w=0.25$ with a power.95 and a significance error of the null hypothesis $\alpha=0.05$.

The procedure used to account for missing, unused and erroneous data will be the "*Pairwise Delection*" method. The confidence intervals of the statistics will be 95% and the contrasts will be performed at a significance level of 5%. All analyses will be performed with the free software R (version 4.1.2+, R Core Team, Vienna, <https://www.R-project.org/>) and the RStudio interface (version 1.4.1103+).

The study will have no planned intermediate analyses as no partial analysis of results is envisaged. Once all data have been collected, verified and validated, a statistical analysis of the data will be performed according to the specifications described in the protocol. If this analysis leads to the conclusion that further analysis is necessary, this will be reported in the final analysis of results. All treated and evaluable subjects shall be analysed. Different statistical tools will be used depending on the nature of the variables collected in the study, accompanying the results with their corresponding graphs.

Lilliefors-Kolmogorov-Smirnov and Shapiro-Wilks tests shall be performed to study the normality of the distribution of quantitative variables, and to their distribution they shall be represented by the mean (standard deviation) or the median (median deviation) and may be accompanied by their corresponding confidence intervals. The relationship between such variables shall be measured with Pearson's or Spearman's correlation coefficients.

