The distributions of the categorical variables will be studied by means of frequencies and percentages. To represent and measure the dependence between them, contingency tables will be used with Pearson's Chi-square test, Fisher's exact test, McNemar's test

or Cochran's Q. A category comparison study could also be done using odds ratios between categories of clinical interest. To study the influence that some categorical variables might have on quantitative variables, ANOVA tests could be performed.

Finally, all the statistical information obtained on the relevance of each variable in the study could be used to apply classification tools to the individuals in the study (decision trees, logistic regression, ROC curves).

22. Direct Access to Source Data/Documents

The Promoter will enter into appropriate arrangements to appoint a monitor to oversee this study and to liaise regularly with the site, including arranging site visits. The investigator agrees to allow the monitor direct access to all relevant documents and to give his/her time and that of his/her staff to the monitor to discuss the results and any issues of concern.

23. Quality Control and Quality Assurance

In order to ensure the quality of the data, the promoter:

- Provide quality instruction and training to the research staff prior to the start of the study. Training topics include, but are not limited to: Good Clinical Practice (GCP) certificates, Adverse Event (AE) reporting, study details and procedures, study documentation, informed consent, and patient recruitment.

- Conduct regular monitoring in accordance with the International Conference on Harmonisation (ICH) for Good Clinical Practice (GCP). Data will be assessed for compliance with the protocol and for accuracy in relation to the source documents. Monitors will verify that the clinical trial is conducted, that data are generated, documented and reported in compliance with the protocol, good clinical practice and any applicable local regulatory requirements.

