DOTIG CLINICAL TRIAL (NCT05419947) STATISTICAL ANALYSIS

Study promoter	Castilla y Institute of Health Sciences Studies Foundation (IECSCYL)- Institute of Biomedical Research of Salamanca (IBSAL)	
EUDRA CT number	2022-000904-36	
Promoter's Protocol Code	IBS-DOTIG-ECM-2202	
Title	Randomised clinical trial to evaluate the dose and time of administration of indocyanine green in near-infrared fluorescein cholangiography during laparoscopic cholecystectomy.	
Date	16/12/2022	

1. Working hypothesis. There are differences in the visualisation rates of extrahepatic biliary structures as a function of drug dose and time of administration.

To test the hypothesis, we created four intervention groups combining two doses (fixed dose of 2.5 mg and weight-adjusted dose ratio of 0.05 mg/kg body weight) and two administration times (15-30 minutes preoperatively and >3 hours preoperatively). The primary endpoints are dichotomous and polytomous qualitative variables.

Before analysing the main and secondary objectives, the groups (G1, G2, G3, G4) and their baseline characteristics should be compared in order to demonstrate that they are homogeneous and the randomisation has been correct. To do this, the following variables collected in the CRDe should be compared:

- Sex (male/female)
- Age (years)
- BMI (kg/m2)
- ASA classification (ASA I/II/III/IV/IV/V)
- Previous abdominal surgeries (NO/SI). In the YES group, break down the variables biliary/liver/pancreas/intestinal/other).
- Previous liver disease (NO/SI). In the SI group, break down the variables: fatty liver disease, hepatitis, liver cirrhosis.
- Previous biliary examinations (NO/SI). In the SI group, break down the ERCP/CTPH variables.
- Previous biliary prostheses (NO/YES)
- Previous acute cholecystitis (NO/SI).
- Previous acute cholangitis (NO/SI).

- Previous gallbladder drainage (NO/SI). In the SI group, break down the variables percutaneous cholecystostomy/endoscopic cholecystostomy.
- Indication for surgery (biliary colic/acute cholecystitis/choledocholithiasis/acute cholangitis/acute lithiasic pancreatitis/bladder polyps/bladder adenomyomatosis).
- Type of surgery (elective/early/deferred surgery). Probably in this variable we do not have a very similar N, because most of them, at least in our centre, were elective.
- Grade of cholecystitis (1/2/3). In case of early indication/delayed urgency.
- Imaging system (Olympus/Karl-Storz/Stryker)
- Type of optics (30 degrees/ 0 degrees).

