- 2. Main objective. To analyse whether there are differences between different doses (single dose and weight-adjusted dose) and different VI administration intervals in the visualisation rates of extrahepatic biliary structures.

Carry out a comparative analysis between the different groups (G1/G2/G3/G4) and the following qualitative variables:

- Identification of biliary structures prior to dissection of the hepatocystic triangle.

o Identification of cystic duct (yes/no).

o Identification of common bile duct (Y/N).

 ${\bf o}$ Identification of the junction of the cystic duct with the common bile duct (Y/N).

- **o** Identification of the junction of the cystic duct with the gall bladder (Y/N).
- **o** Identification of the common hepatic duct (Y/N).
- o Identification of anatomical variables (yes/no).

- Identification of biliary structures after dissection of the hepatocystic triangle.

o Identification of cystic duct (yes/no).
o Identification of common bile duct (Y/N).
o Identification of the junction of the cystic duct with the common bile duct (Y/N).

o Identification of the junction of the cystic duct with the gall bladder (yes/no).

o Identification of the common hepatic duct (Y/N).

o Identification of anatomical variables (yes/no.).

- Degree of identification of biliary structures prior to dissection of the hepatocystic triangle
 - 1=slightly 2=sufficient 3=quite a lot 4=good 5=excellent
- Degree of identification of biliary structures after dissection of the hepatocystic triangle:
 - 1=slightly 2=sufficient 3=quite a lot 4=good 5=excellent
- Extent to which fluorescence cholangiography was perceived to be useful for surgery
 - Not useful Moderately useful Very useful
- Extent to which the fluorescence of the liver background (contrast between liver and ducts) was perceived as disturbing.

0=absence of disturbance 1=slightly disturbed 2=disturbed visualisation, but cystic-choledochal junction was clearly visible before dissection 3= visualisation disturbed and the cystic-choledochal junction was visible only after dissection 4= very disturbed: it was impossible to visualise the biliary structures correctly.

3. Secondary objectives.

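### The stated 95% power at w = 0.25 with 200 patients fits only a 1-df test; the planned four-group comparisons have about 86%, 76% and 62%

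*Protocol*

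**What the plan says.** Protocol section 21 (Statistics) first reaches the sample size from recruitment. It "estimated an average annual number of laparoscopic cholecystectomies of 300 cases. Assuming a minimum recruitment rate of 50% in the study", allows for 12 months and an unquantified loss of patients, and concludes "we estimate a sample size of 200 patients". It then recalls that the main objective is to compare doses and administration times across the four treatment groups on categorical variables. For those it states that the effect "in this type of variables is $w=0.25$ with a power.95 and a significance error of the null hypothesis" of 0.05. No degrees of freedom, table size or specific contrast is given.

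The analysis that this sentence should describe is set out elsewhere:

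- SAP section 1: "The primary endpoints are dichotomous and polytomous qualitative variables".
- SAP section 2: "Carry out a comparative analysis between the different groups (G1/G2/G3/G4) and the following qualitative variables". The list that follows matches the primary variables in protocol section 9.
- Protocol section 21, on categorical variables: "To represent and measure the dependence between them, contingency tables will be used with" Pearson's chi-square, Fisher's exact test and two paired-data tests.
- Analysis set, section 21: "All treated and evaluable subjects shall be analysed". The protocol summary says: "Patients will be analysed per protocol, without intermediate analyses".

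**The concern.** Cohen's w is the effect size of the chi-square test. At a fixed w and n, the power of that test falls as its degrees of freedom rise, so a single power figure cannot hold for yes/no, three-level and five-level variables compared across four groups. The value 0.95 looked too high for any of them.

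This sentence is the only statement in either document of what 200 patients can detect. If it is wrong, a null result would be read as having carried a 5% risk of missing the stated effect when the real risk was several times larger. The error is greatest for the graded scales, and the four graded variables are the only efficacy parameters listed in protocol section 19.

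**Working it through.** **Inputs**

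- n = 200, w = 0.25, alpha = 0.05, stated power 0.95 (protocol section 21).
- Four groups, allocated 1:1:1:1 (section 18), so 50 per group.
- Sixteen primary variables (protocol section 9, SAP section 2): 6 yes/no items before dissection and 6 after, giving 12; one three-level usefulness item; three five-level scales (identification before dissection, identification after it, and liver background).

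**Degrees of freedom**, (rows − 1) × (columns − 1):

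- yes/no: 3 × 1 = 3
- three-level: 3 × 2 = 6
- five-level: 3 × 4 = 12

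**Formula.** Noncentrality λ = n·w² = 200 × 0.0625 = 12.5. Power = P[χ²(df, λ) > the 0.95 quantile of the central χ²(df)].

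**The plan's own figure.** With 1 df the critical value is 3.841 and power is 0.942. Solving for w at power 0.95 and n = 200 gives 0.2549, which prints as 0.25. The stated pair is therefore what a 2x2 calculation returns. No table with more than 1 df comes within two percentage points of 0.95.

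**The planned four-group tables**

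| Variable type | df | Critical value | Power, n = 200 | Chance of missing w = 0.25 | w detectable at 95% | n for 95% at w = 0.25 |
|---|---|---|---|---|---|---|
| (2x2, for reference) | 1 | 3.841 | 0.942 | 6% | 0.255 | 208 |
| Yes/no (12 items) | 3 | 7.815 | 0.856 | 14% | 0.293 | 275 |
| Three-level (1 item) | 6 | 12.592 | 0.758 | 24% | 0.323 | 334 |
| Five-level (3 scales) | 12 | 21.026 | 0.623 | 38% | 0.360 | 414 |

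**Check by simulation.** Pearson's test without continuity correction was simulated with 50 per group and an effect of timing only, scaled to w = 0.25. It rejected in 86.6% (4x2), 76.8% (4x3) and 62.2% (4x5) of trials. A 2x2 table with 100 per arm gave 95.0%. Other patterns of rates in the 4x2 table gave 86% to 89%.

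**Scale of w.** For a yes/no item with an assumed mean rate of 70% and an effect of timing only, the deviation from the mean is 0.25 × √(0.70 × 0.30) = 0.115. So w = 0.25 means 58.5% versus 81.5%.

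**Sensitivity to losses.** The documents give no loss rate, so the rates below are assumptions.

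| Evaluable n | 3 df | 6 df | 12 df |
|---|---|---|---|
| 200 | 0.856 | 0.758 | 0.623 |
| 190 (5% lost) | 0.836 | 0.733 | 0.595 |
| 180 (10%) | 0.814 | 0.705 | 0.566 |
| 170 (15%) | 0.789 | 0.675 | 0.536 |
| 160 (20%) | 0.761 | 0.644 | 0.505 |

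**Recruitment inputs (side point).** If 300 is the trial total, 50% gives 300 × 0.5 = 150, and reaching 200 needs 200/300 = 67%. If 300 is per centre and there are two centres (an assumption), 50% gives 2 × 300 × 0.5 = 300 before losses. The 200 cannot be reproduced without knowing which applies and what loss was allowed.

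**The case against.** The best defence is that the power statement refers to the two factors and not to the four groups. The objective speaks of doses and of administration intervals, and the SAP hypothesis speaks of differences by dose and by time. Each factor compares 100 with 100, which is 1 df for a yes/no item, and the detectable w of 0.2549 then agrees with the printed 0.25. This is a plausible origin for the figure, and since section 21 gives no degrees of freedom, the origin can only be inferred. It does not rescue the statement. The same sentence in section 21 names the four groups, SAP section 2 compares G1 to G4, and no marginal test is planned in either document. Even as main effects, the three-level item (2 df) would have 90% power and the five-level scales (4 df) 82%.

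Three further points have some force:

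- The SAP names no test for the graded scales, so 76% and 62% assume the unordered Pearson test. That is the natural reading, because w belongs to that test and section 21 names it. A test that uses the ordering could have more power, but none is specified for the group comparison.
- A w of 0.25 is not the same clinical difference in 4x2, 4x3 and 4x5 tables. It is held constant here because the protocol applies it to all categorical variables.
- The 50% recruitment rate is described as a minimum, so 200 does not contradict 150. The recruitment point is a request for missing detail and carries no weight in the conclusion.

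**Conclusion.** The concern holds. The stated 95% power is not delivered by any of the planned four-group tests. At the protocol's own w = 0.25, alpha = 0.05 and 200 evaluable patients, power is about 86% for the 12 yes/no items, 76% for the usefulness item and 62% for the three five-level scales.

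These figures rest on the large-sample noncentral chi-square approximation, equal groups, the unordered Pearson test, and alpha of 0.05 for each variable without adjustment for there being 16 of them. Losses or a multiplicity adjustment would lower them. Whether 200 counts randomised or evaluable patients is not stated, so the true position may be worse. The yes/no shortfall, 86% against 95%, is the firmest part, since it depends least on the choice of test.

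**What to change.** Replace the power sentence in section 21, leaving n as it is, with text to this effect:

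> With 200 evaluable patients (50 per group) and alpha 0.05 per test, unadjusted for the number of primary variables, Pearson's chi-square test across the four groups has 86% power to detect w = 0.25 for yes/no variables (3 df), 76% for the three-level variable (6 df) and 62% for the five-level variables (12 df). The effect detectable with 95% power is w = 0.29, 0.32 and 0.36 respectively.

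Then:

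- State whether 200 means randomised or evaluable, and give the assumed loss. If 200 are randomised and 10% are lost (n = 180), the powers become 81%, 70.5% and 57%, and the detectable w at 95% power becomes 0.31, 0.34 and 0.38.
- If a main-effect contrast of 100 versus 100 on a yes/no item was intended, name it as primary in both documents and claim 94% for that contrast only.
- If a different test is intended for the graded scales, name it and give its own power.
- In the recruitment sentence, say whether 300 is per centre or in total, how many centres contribute, and what loss was allowed.

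The cost is one reworded paragraph and a less favourable stated power. Patient handling and the sample size do not change. The wording does tie the graded scales to the chi-square test for the group comparison, which the SAP currently leaves unnamed.

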In these secondary objectives, we tried to analyse predictors of the quality of the fluorescence technique. To this end, we have found numerous factors in the literature that could influence cholangiography. We want to show whether there are differences between the factors listed below and the different working groups.

a) To analyse the influence of body mass index on FC outcomes during CL.

In this section, we could recode the qualitative variable BMI into the different BMI subgroups defined by the World Health Organisation or use normal weight/overweight as the cut-off point.

Clasificación	IMC (Kg/m ²
Normal	18.5 - 24.9
Sobrepeso	25 - 29.9
Obesidad grado I	30 - 34.9
Obesidad grado II	35 - 39.9
Obesidad grado III	Más de 40

We could also analyse it as a quantitative variable and see if there is a correlation between them.

b) To analyse the influence of the type of biliary pathology requiring surgery and previous liver disease on the results of FC during LC.

Analyse whether there are differences between "Previous liver disease (NO/SI). In the SI group, break down the variables: fatty liver disease, hepatitis, liver cirrhosis". And the main variables shown.

c) To analyse the influence of the type of surgery (elective/early/ delayed surgery) on the results of FC during LC.

To analyse whether there are differences between the variables "type of surgery" and "indication for surgery".

d) To analyse the influence of previous gallbladder or bile duct instrumentation on the results of FC during LC.

To analyse whether there are differences between the variables "previous biliary explorations", "previous biliary prostheses" and "previous gallbladder drainage". Both separately and united in a single variable.

e) To analyse the influence of different laparoscopic imaging systems on the results of FC during LC.

To analyse whether there are differences between the variable "image system" and the main target variables.

f) To analyse the rate of intraoperative complications related to CF during LC.

To analyse intraoperative complication rates in the series.

g) To analyse the rate of postoperative complications related to CF during LC.

To analyse the postoperative complication rate for the series overall and for each type of Clavien-Dindo classification (consecutive variable).

Also to analyse separately the rate of bile duct injury and the characteristics of bile duct injuries (consecutive variables).

Analyse in-hospital and 30-day mortality rates.

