h) To analyse the impact of FC during LC on general surgeons and/or surgeons specialised in hepatobiliopancreatic pathology and their subjective assessment of the procedure.

To analyse this secondary objective, we should analyse globally the primary variable detailed above "Extent to which fluorescence cholangiography was perceived to be useful for surgery". We should also analyse it individually in each group.

- i) Analyse the rate and characteristics of late adverse reactions and AEs (separate Excel).
- j) To analyse the rate of anatomical variables (for this purpose we only analysed the variables (identification of biliary anatomical variables prior to dissection and the variable identification of biliary anatomical variables after dissection) globally.
- k) To analyse the influence of the technique on surgical time. To do so, we analysed the median complete surgical time (variable surgical time).

Note: in the study protocol we have put "Finally, all the statistical information obtained about the relevance of each variable in the study could be used to apply classification tools to the individuals in the study (decision trees, logistic regression, ROC curves)". I think this is a very interesting aspect but I need to talk about it and I need you to explain this section to me

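### If the optional classification step is carried out as worded, variables are chosen and models judged on the same patients with no validation, so its ROC curves will be optimistic

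*Protocol*

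**What the plan says.** The last paragraph of the statistical methods in Protocol section 21 describes a possible final step. Its input is the trial's own findings: "all the statistical information obtained on the relevance of each variable in the study could be used to apply classification tools". Its target is the trial's own patients, since this information "could be used to apply classification tools to the individuals in the study (decision trees, logistic regression, ROC curves". The verb is conditional, so the step is an option.

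The note that ends SAP section 3 copies this sentence and then addresses the analyst: "I think this is a very interesting aspect but I need to talk about it", followed by "I need you to explain this section to me". Nothing is settled there.

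The nearest statement of purpose is the introduction to SAP section 3, which says of the secondary objectives that "we tried to analyse predictors of the quality of the fluorescence technique". The same paragraph gives the origin of the factors: "we have found numerous factors in the literature that could influence cholangiography".

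Neither document states which outcome would be classified, which variables are candidates, how they would be selected, or how performance would be checked. No hold-out set, cross-validation, bootstrap correction or outside cohort is mentioned.

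**The concern.** A model is flattered when it is tested on the patients used to choose its variables and estimate its coefficients. Chance associations that led to a variable being picked are counted again as predictive performance, so the apparent AUC is biased upward. The bias grows with the number of variables tried, the flexibility of the model and the rarity of the less common outcome.

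The wording also leaves the target open. SAP section 2 lists twelve yes/no identification variables and four graded scales, sixteen in all, and any of them could be taken as the outcome once the data have been seen.

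What is at stake is a secondary message: a curve suggesting that certain patients give good or poor cholangiograms when that may be noise.

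**Working it through.** The plan gives no figure for this step. The only calculation in Protocol section 21 is a chi-square power statement, which does not concern classification. The check therefore asks what same-patient AUC would be seen if no candidate were related to the outcome (true AUC 0.50).

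**Inputs from the documents**
- n = 200 and a 5% significance level (Protocol section 21).
- Candidates: the 16 variables in SAP section 1 under "the following variables collected in the CRDe should be compared", plus intervention group, giving 17. The documents give no candidate list for the models, so using this list is an assumption.

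**Assumed inputs**
- Outcome present in 50%, 70% or 90% of patients, so the rarer class is 50%, 30% or 10%. The documents give no expected rates.
- Category frequencies for each variable, coded as 26 model terms.
- Trees of depth 3 or 4 with at least 7 patients per leaf.

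**Step 1. Chance of at least one falsely relevant variable.** For 17 independent null tests:
- at 5%: 1 − 0.95^17 = 1 − 0.418 = 0.58
- at 10%: 1 − 0.90^17 = 1 − 0.167 = 0.83

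**Step 2. Null simulation.** There were 300 data sets per outcome rate. Variables were screened one at a time and a logistic model was fitted to those selected; alternatively, all 17 were forced in, or a tree was grown. AUC was computed on the same 200 patients and on 1,000 new ones.

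| Route | Mean same-patient AUC at 50% / 70% / 90% | Runs with AUC of at least 0.70 |
|---|---|---|
| Screened at p<0.05, when anything is selected | 0.60 / 0.61 / 0.65 | 0% / 2% / 12% |
| Screened at p<0.20, when anything is selected | 0.64 / 0.65 / 0.72 | 9% / 16% / 63% |
| All 17 forced in | 0.71 / 0.72 / 0.83 | 58% / 77% / over 99% |
| Tree, depth 3 | 0.68 / 0.69 / 0.78 | 29% / 43% / 94% |
| Tree, depth 4 | 0.73 / 0.74 / 0.84 | 73% / 82% / 99% |

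The last column counts all runs, including those in which nothing was selected. At p<0.05 that was 41%, 43% and 48% of runs. Mean AUC in new patients was 0.50 on every route.

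**Step 3. Second null simulation.** With 24 model terms and its own assumed frequencies and rates, mean same-patient AUC was about 0.60 to 0.67 after p<0.05 screening (nothing selected in 38% to 46% of runs), 0.61 to 0.69 after p<0.10 screening, and 0.70 to 0.83 with all factors forced in. The two simulations agree closely.

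**Step 4. Why the outcome rate matters.** At 10%, the rarer class has 0.10 × 200 = 20 patients for 26 terms, or 20/26 = 0.8 per term. At 50% it has 100 patients, or 100/26 = 3.8 per term. Both are few, and the first is much worse.

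Choosing among the sixteen possible outcomes after seeing the data was not simulated. It would add to the optimism.

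**The case against.** The strongest reply is that this is not yet a plan. The protocol only allows the step, and the SAP author asks for it to be explained. The factors behind the predictor objectives come from the literature, so the starting list was not picked from trial results. No p-value screening rule is written down. The outcome, fluorescence quality, is inferred from SAP section 3, because Protocol section 21 names none. Nothing says that a prediction rule will be published or used to select patients.

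Most of this stands, and it is why the point is conditional. It does not remove the problem. A literature-based starting list limits the candidates, but the protocol sentence still brings in relevance found in this trial, and no validation is named for whatever model follows.

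A reader might infer more than the documents support:
- **That the ROC curves are bound to look good even if nothing predicts.** At the plan's only stated level, 5%, mean null AUC is about 0.60 to 0.67 when a model exists, and in roughly 40% to 45% of runs there is none. Values of 0.70 and above are typical only with looser rules, all factors forced in, deeper trees or a rare outcome class.
- **That trees should be banned or penalised regression required.** The simulated trees were optimistic, which is a reason to validate them. The choice of model is a preference.
- **That the trial's main result is at risk.** The four-group comparison does not use this step.

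**Conclusion.** The concern holds in conditional form. If the step is done as worded, its ROC curves will be optimistic and can suggest useful prediction when there is none. The average excess over a true AUC of 0.50 is about 0.10 to 0.17 after p<0.05 screening when anything is selected, 0.11 to 0.19 after p<0.10 screening, and 0.20 to 0.33 with all listed factors forced in.

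These sizes rest on n = 200, event rates of 10% to 50%, assumed category frequencies, candidates taken from the SAP baseline list, and fluorescence quality as the outcome. The p<0.10 and p<0.20 thresholds are illustrative and appear in neither document. The direction of the bias was the same in every scenario tried. This is a weakness in an exploratory, undecided part of the analysis. It is cheap to close before the models are run, and the SAP note has to be resolved in any case.

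**What to change.** Take one of two courses in Protocol section 21 and the SAP's closing note.

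1. Delete the sentence.
2. Keep the step and specify it:
   - label it exploratory;
   - name one outcome and a candidate list in advance, for example the literature-based factors in SAP section 3;
   - state any selection rule;
   - report AUC only after internal validation, by bootstrap optimism correction or cross-validation, with every selection and fitting step, including any tree, repeated inside each resample.

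The cost is a short change of wording, a few lines of R and a less favourable reported AUC. No extra patients or data are needed, and the primary analysis does not change.
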